# 7.3 Center Pooling

Data will be pooled for analysis. Additional sensitivity analysis will be performed for site effect in section 7.9.4.

# 7.4 Handling of Missing, Unused, and Spurious Data and Dropouts

20-DEC-2023 Revision 3.0 Page 17 of 25

For the primary safety analysis (change of HbA1c), if HbA1c at end of study is not available in subjects, missing data in HbA1c measurements will be handled by the multiple imputation approach using imputation regression method. The independent variables in the regression model are age, gender, baseline HbA1c, diabetes duration, BMI. The imputation will be performed five times and the analysis results will be combined to form one inference in SAS.

For partial date stated in Medical history, the first day of the month or the first day of the year will be used.

For visit 13 date is missing and subjects exited after visit 7 + 44 days, the date of visit 7 + 44 days will be used for cut-off dates in analysis. No imputation for CGM related endpoints will be performed.

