## **CIP335 Clinical Investigation Plan** Medtronic Version E Page 50 of 106 D00409632

If the subject visits the investigational center outside of the scheduled study visits, a Visit eCRF will be completed to document the reason for the unscheduled visit.

[figure not shown]
Refer to **Section 9.1.1**, **Table 3** for the Visit Details.

If subject exits the study early (i.e., before their last scheduled visit), HbA1c requirements that apply to the final visit will be completed for subjects who have completed Visit 7. Refer to CIP335 Lyumjev -Questionnaire Guide for collection of early exit questionnaire requirements.

The Exit eCRF and all associated activities should be completed for all subjects who have withdrawn, discontinued, or completed the study.

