#### 9.5.4 HbA1c

HbA1c is collected at baseline and the end of subjects' participation; if subjects have completed Visit 7 and exit early, a HbA1c will be collected. For subjects 21 years of age and older, HbA1c will also be collected at Visit 7, 12 and 14.

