# 9.7 Deviation Handling

A deviation is any instance(s) of failure to follow, intentionally or unintentionally, the requirements of the CIP. It is expected that the investigator will conduct this clinical trial in compliance with the CIP and all applicable regulations governing the conduct of clinical research involving human subjects. Failure to do so could result in one or all of the following:

- Investigational center disqualification
- · Notification to the regulatory authorities/IRB depending on the severity of the deviation and reporting requirements

The investigator should not implement any deviation from, or changes to, the CIP without agreement by the sponsor and prior review and documented approval/favorable opinion from the regulatory authority (if applicable) or IRB, except where necessary to eliminate an immediate hazard(s) to subjects. The use of waivers from the CIP are prohibited in this study.

Subjects 21 years of age and older are asked for an HbA1c test at Visit 1, Visit 7, Visit 12, Visit 14 and Visit 15. Failing to take the test at Visits 1 and 15 will result in a deviation. Failing to take the test at visits 7, 12 and 14 will not be subject to a deviation.

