### 14.6 Handling Missing Data

For the primary safety analysis (change of HbA1c), if HbA1c at end of study is not available in subjects, missing data in HbA1c measurements will be handled by the multiple imputation approach using imputation regression method. The independent variables in the regression model are age, gender, baseline HbA1c, diabetes duration, BMI. The imputation will be performed five times and the analysis results will be combined to form one inference in SAS.

No imputation for CGM related endpoints will be performed.

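### The imputation model for the primary HbA1c endpoint uses baseline variables only and omits on-study sensor glucose, so it cannot correct for missingness that depends on on-study control

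*SAP*

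**What the plan says.** SAP 7.4 triggers imputation "if HbA1c at end of study is not available in subjects". It then fixes the model: "The independent variables in the regression model are age, gender, baseline HbA1c, diabetes duration, BMI". Protocol 14.6 lists the same predictors. On the number of draws, the SAP states: "The imputation will be performed five times and the analysis results will be combined to form one inference in SAS".

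Three other provisions bear on this.

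- **Exit sample.** Protocol 9.5.4 provides that "if subjects have completed Visit 7 and exit early, a HbA1c will be collected", and Protocol 9.1 that "HbA1c requirements that apply to the final visit will be completed for subjects who have completed Visit 7". The SAP does not say whether such a value is the end-of-study HbA1c.
- **Interim HbA1c.** Protocol 9.5.4: "For subjects 21 years of age and older, HbA1c will also be collected at Visit 7, 12 and 14". Protocol 9.7 adds: "Failing to take the test at visits 7, 12 and 14 will not be subject to a deviation".
- **Sensor glucose.** The study pump collects it (Protocol 9.5.3), and Protocol Table 3 requires weekly pump uploads, with no age restriction.

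The sensitivity analyses in SAP 7.9.4 are the per-protocol set, which contains completers only, and a site-effect analysis. Neither varies the missing-data assumption.

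**The concern.** Multiple imputation from baseline variables is unbiased only if, among subjects with the same baseline profile, those with a missing HbA1c would have done as well as those with a measured one. On-study glucose control is an obvious way for that to fail, and Protocol 9.8 ties some withdrawals to on-study events such as SmartGuard-related DKA. The trial holds a direct on-study measure of control for every age group, and the model does not use it.

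HbA1c change is the primary safety endpoint. SAP 7.9.1 makes it necessary for success in each age cohort, and SAP 7.5 puts it first in the fixed sequence, so every later test depends on it.

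**Working it through.** **The plan's own figure.** Inputs from Protocol 14.5 and SAP 6.2: n = 80, SD 0.7%, true mean equal to the threshold, margin 0.4%, one-sided level 0.025. Standard error = 0.7/√80 = 0.0783. Distance to the boundary in standard errors = 0.4/0.0783 = 5.11. Exact one-sample t power is 99.9% (normal approximation: Φ(5.11 − 1.96) = 99.9%). The stated figure of more than 80% is correct as a lower bound; 80% power needs 27 subjects.

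**Boundaries.** Adults: −0.50 + 0.40 = −0.10%. Ages 7-17: −0.38 + 0.40 = +0.02%. Both lie 0.4 points from the design mean with the same SD, so a given bias has the same effect on the test in either cohort.

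**Bias by arithmetic.** Let p be the share with no usable HbA1c and δ the amount by which they are truly worse than completers with the same baseline profile. Then bias ≈ −p × δ. Type I error is the t-test's rejection rate when the mean is shifted by that bias, here at n = 100 (standard error 0.07):

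| p | δ | bias | type I error |
|---|---|---|---|
| 5% | 0.25 | −0.013 | 3.7% |
| 10% | 0.50 | −0.05 | 10.5% |
| 20% | 0.50 | −0.10 | 29.3% |

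This ignores the variance that imputation adds.

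**Bias by simulation.** Regression imputation with five draws, results combined by Rubin's rules, n = 100, 4,000 runs per row, true mean at the adult boundary. The documents give no rate of missing HbA1c after the study period starts (Protocol 14.5.3 covers only 250 enrolled for 200 entering). These inputs are therefore assumptions: 5%, 10% or 20% missing; baseline HbA1c mean 7.5%, SD 0.9%; slope of change on baseline −0.4, giving residual SD √(0.49 − 0.36²) = 0.60; correlation ρ of 0.6 or 0.8 between on-study glycemia and that residual; log-odds of missingness rising by 1 per SD of on-study glycemia. Missing subjects then average 0.31 to 0.44 points worse than completers.

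| ρ | missing | bias, planned model | type I, planned model | type I, on-study glycemia added |
|---|---|---|---|---|
| 0.6 | 5% | −0.017 | 4.2% | 2.4% |
| 0.6 | 10% | −0.032 | 6.2% | 2.2% |
| 0.6 | 20% | −0.065 | 13.1% | 2.6% |
| 0.8 | 5% | −0.023 | 5.0% | 2.5% |
| 0.8 | 10% | −0.042 | 8.8% | 2.5% |
| 0.8 | 20% | −0.083 | 18.9% | 2.6% |

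With the covariate added, bias is within 0.002 in every row. Simulation error on a 2.5% rate is √(0.025 × 0.975/4000) = 0.25 percentage points. The bias agrees with p × δ; in the last row, 0.20 × 0.42 = 0.084.

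**Effect on the likely result.** At n = 100 the adult test passes if the estimated mean is below −0.10 − 1.984 × 0.07 = −0.24%. From −0.50% that leaves about 0.26 points of slack. To use it up, missing subjects would have to be 0.26/0.20 = 1.3 points worse at 20% missing, or 0.26/0.10 = 2.6 points worse at 10%. In 1,000 simulated runs at the design mean with 20% missing and ρ = 0.8, both models passed every time.

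**The case against.** The strongest reply is that leaving early does not make the outcome missing. The intention-to-treat set starts with the study period, and anyone who exits after Visit 7 is due an HbA1c. A footnote to Protocol Table 3 applies all final-visit requirements at early exit, and the table allows mobile phlebotomy when the final visit is virtual. This stands. Only subjects with no usable value are imputed, and the missing rates above may be too high. It does not settle the matter, because the SAP never says that the exit value counts.

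Four further points also stand.

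- A reader might infer that early leavers are treated as average completers. They are not: values are drawn conditional on the five baseline variables.
- A reader might infer that the bias must favor success. DKA points to high glucose, but severe hypoglycemia need not. Infusion-site reactions are graded on pain, erythema and pruritus (Protocol 11.2), not on glycemia.
- A reader might expect the interim HbA1c values to solve the problem. They do not exist for ages 7-17 or 18-20, and they may be skipped without a deviation. The Visit 7 value is taken as Lyumjev starts, so it reflects control before treatment.
- The simulation generates missingness from the same variable that it then adds. Removal of the bias is therefore built in, and says nothing about how missingness will arise in this trial.

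The SAP's bar on imputing CGM endpoints is not an obstacle: it does not prevent the use of sensor glucose as a predictor.

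**Conclusion.** The point holds as a weakness in the imputation model for a gating endpoint. The model relies on missing at random given baseline alone, omits on-study glycemia that the trial collects in both cohorts, and has no sensitivity analysis behind it. The sizes above, a bias of about −0.02 to −0.08 points and type I error of about 4-19% at the boundary, rest on the assumed missing rates, correlation and missingness mechanism. They show what could happen near the margin and do not forecast this trial.

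The documents do not support a claim that the study's conclusion would change. At the design mean the test has ample slack. Nor is there a shown need for more than five imputations: with the on-study covariate, five draws kept type I error at 2.2-2.6%.

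**What to change.** Amend SAP 7.4 and Protocol 14.6 as follows.

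1. In both cohorts, add on-study mean sensor glucose (or time in range) to the imputation model. Summarize it over the setpoint periods already listed in SAP 7.9.5: Visits 7-11, Visits 11-13, and Visit 13 to exit. Early leavers and completers are then compared over the same periods. Periods that a subject did not reach are imputed in sequence.
2. At age 21 and over, also use Visit 12 and Visit 14 HbA1c where present, imputed in sequence.
3. State whether an early-exit HbA1c counts as the end-of-study value. Do not use it as a predictor: completers aged 7-17 have HbA1c only at Visits 1 and 15, so no coefficient for an intermediate value could be estimated in that cohort.
4. Add a delta-adjusted tipping-point analysis for the imputed values. This addresses missingness that depends on more than the measured covariates.

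The cost is revised wording and a small amount of programming. No new data are needed.

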## 7.5 Adjustments for Multiple Comparisons

The following hierarchical test procedure reflects the relative importance of the endpoints and controls for multiplicity. Safety and effectiveness endpoints will be evaluated independently between age 18-80 and age 7-17.

Fixed sequential testing of primary safety, primary effectiveness and secondary effectiveness endpoints for age 18-80 and age 7-17.

## 7.5.1 Age 18-80

For the following endpoints from age 18-80, the procedure test hierarchically the ordered hypotheses in sequence at level a=0.025 until a first hypothesis is non-rejected.

## **Primary Safety Endpoint**

Age 18-80: The overall mean change in HbA1c from baseline to end of 3-month study period. The mean change will be estimated and compared to a threshold of -0.5% with a margin of 0.4%.

### **Primary Effectiveness Endpoint**

Age 18-80: The mean % of time in range (TIR 70-180 mg/dL) will be estimated and compared to a threshold of 73.7% with a margin of -7.5% and a significance level of 0.025 (one-sided).

### **Secondary Effectiveness Endpoints**

- Age 18-80: The mean % of time in hypoglycemia (< 54 mg/dL) will be estimated and compared to a threshold of 0.86% with a margin of 2% and a significance level of 0.025 (one-sided).
- Age 18-80: The mean % of time in range (TIR 70-180 mg/dL) will be estimated and compared to a threshold of 73.7% and a significance level of 0.025 (one-sided).

### 7.5.2 Age 7-17

### **CIP335 Statistical Analysis Plan Form** Medtronic 20-DEC-2023 Revision 3.0 Page 18 of 25

For the following endpoints from age 7-17, the procedure test hierarchically the ordered hypotheses in sequence at level a=0.025 until a first hypothesis is non-rejected.

## **Primary Safety Endpoint**

 Age 7-17: The overall mean change in HbA1c from baseline to end of 3-month study period. The mean change will be estimated and compared to a threshold of -0.38% with a margin of 0.4%.

## **Primary Effectiveness Endpoint**

Age 7-17: The mean % of time in range (TIR 70-180 mg/dL) will be estimated and compared to a threshold of 65.3% with a margin of -7.5% and a significance level of 0.025 (one-sided).

## **Secondary Effectiveness Endpoints**

- Age 7-17: The mean % of time in hypoglycemia (< 54 mg/dL) will be estimated and compared to a threshold of 0.71% with a margin of 2% and a significance level of 0.025 (one-sided).
- Age 7-17: The mean % of time in range (TIR 70-180 mg/dL) will be estimated and compared to a threshold of 65.3% and a significance level of 0.025 (one-sided).

# 7.6 Demographic and Other Baseline Characteristics

Subject characteristics, including age, gender, race, ethnicity, medical diagnosis, height, weight, Body Mass Index (BMI), and baseline HbA1c will be summarized by descriptive statistics (mean, standard deviation, minimum, median, and maximum) for continuous variables and by counts and percentages for categorical variables.

## 7.7 Treatment Characteristics

Not applicable.

## 7.8 Interim Analyses

Not applicable.

# 7.9 Evaluation of Objectives

Safety and effectiveness endpoints will be evaluated independently between age 18-80 and age 7-17.

20-DEC-2023 Page 19 of 25 Revision 3.0

## 7.9.1 Pass/Fail Criteria

The study pass/fail criteria is based on statistical hypothesis of the primary endpoints. The study for each age cohort (age 18-80 and age 7-17) will be considered a success when the evaluation criteria of both primary safety and effective endpoints meets the predefined threshold per cohort.

Justification for Exclusion of Particular Information from the testing of the Hypothesis: Not Applicable.

## 7.9.2 Primary Safety Endpoint

### Age 18-80:

The overall mean change in HbA1c,  $\Delta\mu_{780G}$ , from baseline to end of 3-month study period will be estimated and compared to the threshold of -0.50% with a margin of 0.4%. A significance level of 0.025 (one-sided) will be used. Analysis will be performed on the ITT and PP populations.

The hypothesis is mathematically expressed as:

$$H_0$$
:  $\Delta \mu_{780G} \ge -0.50\% + 0.4\%$ 

Ha: 
$$\Delta \mu_{780G} < -0.50\% + 0.4\%$$

The null hypothesis will be tested against the alternative hypothesis using one sample t test if normality assumption is met, Wilcoxon signed rank test if normality assumption is rejected. The mean change in HbA1c from baseline to end of 3-month study period is less than -0.50% with a margin of 0.4% for age 18-80 will be concluded if null hypothesis is rejected.

### Age 7-17:

The overall mean change in HbA1c,  $\Delta\mu_{780G}$ , from baseline to end of 3-month study period will be estimated and compared to the threshold of -0.38% with a margin of 0.4%. A significance level of 0.025 (one-sided) will be used. Analysis will be performed on the ITT and PP populations.

The hypothesis is mathematically expressed as:

$$H_0$$
:  $\Delta \mu_{780G} \ge -0.38\% + 0.4\%$ 

$$H_a$$
:  $\Delta \mu_{780G} < -0.38\% + 0.4\%$ 

### **CIP335 Statistical Analysis Plan Form** Medtronic 20-DEC-2023 Page 20 of 25 Revision 3.0

The null hypothesis will be tested against the alternative hypothesis using one sample t test if normality assumption is met, Wilcoxon signed rank test if normality assumption is rejected. The mean change in HbA1c from baseline to end of 3-month study period is less than -0.38% with a margin of 0.4% for age 7-17 will be concluded if null hypothesis is rejected.

## 7.9.3 Analysis of Effectiveness Endpoint

All effectiveness endpoints will be analyzed using the data from the visit 13 to the end of the study (Auto Basal target set at investigator's discretion).

## 7.9.3.1 Primary Effectiveness Endpoint

### Age 18-80:

The mean % of time, µ780G, in range (TIR 70-180 mg/dL) will be estimated and compared to the threshold of 73.7% with a margin of -7.5%. A significance level of 0.025 (one-sided) will be used. The 7.5%, which is approximately 100 minutes increase in TIR per day, was also observed from the HCL pivotal trials. Analysis will be performed on the ITT and PP populations.

The hypothesis is mathematically expressed as:

H0:  $\mu_{780G} \le 73.7\% - 7.5\%$ 

 $H_a$ :  $\mu_{780G} > 73.7\% - 7.5\%$ 

The null hypothesis will be tested against the alternative hypothesis using one sample t test if normality assumption is met, Wilcoxon signed rank test if normality assumption is rejected. Mean % of time in target from MiniMed 780G system utilizing Lyumjev insulin is greater than 73.7% with a margin of -7.5% for age 18-80 will be concluded if null hypothesis is rejected.

### Age 7-17:

The mean % of time, µ780G, in range (TIR 70-180 mg/dL) will be estimated and compared to the threshold of 65.3% with a margin of -7.5%. A significance level of 0.025 (one-sided) will be used. The 7.5%, which is approximately 100 minutes increase in TIR per day, was also observed from the HCL pivotal trials. Analysis will be performed on the ITT and PP populations.

The hypothesis is mathematically expressed as:

20-DEC-2023 Revision 3.0 Page 21 of 25

Form Medtronic

H0:  $\mu_{780G} \le 65.3\% - 7.5\%$ 

 $H_a$ :  $\mu_{780G} > 65.3\% - 7.5\%$ 

The null hypothesis will be tested against the alternative hypothesis using one sample t test if normality assumption is met, Wilcoxon signed rank test if normality assumption is rejected. Mean % of time in target from MiniMed 780G system utilizing Lyumjev insulin is greater than 65.3% with a margin of -7.5% for age 7-17 will be concluded if null hypothesis is rejected.

## 7.9.3.2 Analysis of Secondary Effectiveness Endpoints

### Age 18-80:

• Secondary Effectiveness Endpoint: The mean % time,  $\mu_{780G}$ , in hypoglycemia (< 54 mg/dL) will be estimated and compared to the threshold of 0.86% with a margin of 2%. A significance level of 0.025 (one-sided) will be used. Analysis will be performed on the ITT and PP populations.

The hypothesis is mathematically expressed as:

 $H_0$ :  $\mu_{780G} \ge 0.86\% + 2\%$ 

 $H_a$ :  $\mu_{780G} < 0.86\% + 2\%$ 

The null hypothesis will be tested against the alternative hypothesis using one sample t test if normality assumption is met, Wilcoxon signed rank test if normality assumption is rejected. Mean % of time below range from MiniMed 780G system utilizing Lyumjev insulin is less than 0.86% with a margin of 2% for age 18-80 will be concluded if null hypothesis is rejected.

• Secondary Effectiveness Endpoint: The mean % of time,  $\mu_{780G}$ , in range (TIR 70-180 mg/dL) will be estimated and compared with a significance level of 0.025 (one-sided). Analysis will be performed on the ITT and PP populations.

[figure not shown]
The hypothesis is mathematically expressed as:

H0:  $\mu_{780G}$  ≤73.7%

 $H_a$ :  $\mu_{780G} > 73.7\%$ 

The null hypothesis will be tested against the alternative hypothesis using one sample t test if normality assumption is met, Wilcoxon signed rank test if normality assumption is rejected. Mean % of time in target from MiniMed 780G system utilizing Lyumjev insulin is greater than 73.7% for age 18-80 will be concluded if null hypothesis is rejected.

20-DEC-2023 Page 22 of 25 Revision 3.0

### Age 7-17:

Secondary Effectiveness Endpoint: The mean % time, µ780G, in hypoglycemia (< 54 mg/dL) will be estimated and compared to the threshold of 0.71% with a margin of 2%. A significance level of 0.025 (one-sided) will be used. Analysis will be performed on the ITT and PP populations.

The hypothesis is mathematically expressed as:

H0:  $\mu_{780G} \ge 0.71\% + 2\%$ 

 $H_a$ :  $\mu_{780G} < 0.71\% + 2\%$ 

The null hypothesis will be tested against the alternative hypothesis using one sample t test if normality assumption is met, Wilcoxon signed rank test if normality assumption is rejected. Mean % of time below range from MiniMed 780G system utilizing Lyumjev insulin is less than 0.71% with a margin of 2% for age 7-17 will be concluded if null hypothesis is rejected.

 Secondary Effectiveness Endpoint: The mean % of time, μ780G, in range (TIR 70-180 mg/dL) will be estimated and compared with a significance level of 0.025 (one-sided). Analysis will be performed on the ITT and PP populations.

The hypothesis is mathematically expressed as:

H0:  $\mu_{780G}$  ≤65.3%

 $H_a$ :  $\mu_{780G} > 65.3\%$ 

[figure not shown]
The null hypothesis will be tested against the alternative hypothesis using one sample t test if normality assumption is met, Wilcoxon signed rank test if normality assumption is rejected. Mean % of time in target from MiniMed 780G system utilizing Lyumjev insulin is greater than 65.3% for age 7-17 will be concluded if null hypothesis is rejected.

## 7.9.4 Sensitivity Analysis for Primary Safety, Primary Effectiveness and **Secondary Effectiveness Endpoints**

## 7.9.4.1 Sensitivity Analysis 1: PP population

Primary safety, primary effectiveness and secondary effectiveness endpoints will be evaluated for PP population as the sensitivity/supplementary analyses.

20-DEC-2023 Page 23 of 25 Revision 3.0

## 7.9.4.2 Sensitivity Analysis 2: Site effect evaluation with ITT population

To address the pooled sites in statistical analysis, sensitivity analysis 2 will be conducted if the site effect is significant (with a significance level of 0.1) in primary safety, primary effectiveness and secondary effectiveness endpoints.

The site effect will be evaluated by a linear mixed model. And the final estimate will be a weighted average of the estimate for each site, where the weight of each site is the inverse of the variance of each site estimate (which equals to the inverse of the square of the standard error of each site estimate).

Note: During the site effect test, all sites with less than 6 subjects per age group will be pooled into one 'Pseudo-site'. If the number of subjects in Pseudo-site is larger than 30, it will be split to two Pseudosites.

